## 11. MEDICAL HISTORY

Medical history is defined as any medical conditions/diseases that started and stopped before screening as well as any medical conditions/diseases that started before screening AND were ongoing at the time of screening.

Medical history will be coded using the Medical Dictionary for Regulatory Activities (MedDRA) version 23.0 or later and will be summarized by System Organ Class and PT overall and by treatment group based on the SAF. A subject having more than one medical condition/disease within the same System Organ Class/PT will be counted only once for that System Organ Class or PT. In the summary, System Organ Classes will be sorted in alphabetical order and within each System Organ Class, PTs will be sorted in decreasing order of total frequency.

## 12. DISEASE HISTORY

The following disease history characteristics will be summarized overall and by treatment group based on the SAF analysis set:

- Time since first COVID-19 symptoms onset (days) – calculated relative to Study Day 1 (refer to [Section 6.1](#));
- Time since COVID-19 diagnosis (days) – calculated relative to Study Day 1;
- Hospitalized at study entry;
- Time since hospital admission (days) – calculated relative to Study Day 1;
- Time since ICU/HDU admission (days) for subjects in ICU/HDU at study entry – calculated relative to Study Day 1;
- Presence and severity of each of the following COVID-19 symptoms at study entry:
  - Cough;
  - Fever;
  - Myalgia;
  - Diarrhea;
  - Dyspnea;

Document: \[REDACTED]\net\enterprise\Apps\sasdata\SASb\SAS\Atea\_Pharmaceuticals\AT-527\SAZ\A63631\Biostatistics\Documentation\SAP\AT-03A-001\_V1.0\_COVID\_SAP\_PA7.doc  
Author: \[REDACTED]

Version Number: V1.0  
Version Date: 15Apr2021

Template No.: CS\_TP\_BS016 Revision 6  
Effective Date: 02Dec2019

Reference: CS\_WI\_BS005

Copyright © 2009, 2010, 2012, 2016, 2018, 2019 \[REDACTED] All rights reserved. The contents of this document are confidential and proprietary to \[REDACTED] Holdings Inc. and its subsidiaries. Unauthorized use, disclosure or reproduction is strictly prohibited.

## COVID-19 Statistical Analysis Plan

ATEA Pharmaceuticals

Protocol AT-03A-001

Page 28 of 77

- Headache;
- Nausea;
- Vomiting;
- Fatigue/malaise;
- Loss of appetite;
- Loss of smell;
- Loss of taste.

All disease history characteristics will be listed.

## 12.1. DERIVATIONS

‘Time since’ disease history characteristics, in days, will be calculated as follows:

- Time since first COVID-19 symptom(s) (days) = (Date of Study Day 1 – Date of first COVID-19 symptom(s) onset); date of onset of COVID-19 symptoms as captured on the Medical History page of the eCRF;
- Time since COVID-19 diagnosis (days) = (Date of Study Day 1 - Date of COVID-19 diagnosis); date of COVID-19 diagnosis as captured on the Medical History page of the eCRF;

## 13. MEDICATIONS

- Prior medications are defined as any medication that started and stopped prior to the date of Study Day 1
- Concomitant medications are defined as:
  - Any medication that started before the date of Study Day 1 AND ended on the date of Study Day 1 or were ongoing at that time;
  - Any medication that started on or after the date of Study Day 1.

Partially or completely missing medication start and stop dates will be handled as described in [APPENDIX 1](#).

Document: \[REDACTED]\net\enterprise\Apps\sasdata\SASb\SAS\Atea\_Pharmaceuticals\AT-527\SAZ\A63631\Biostatistics\Documentation\SAP\AT-03A-001\_V1.0\_COVID\_SAP\_PA7.doc  
Author: \[REDACTED]

Version Number: V1.0  
Version Date: 15Apr2021  
Template No.: CS\_TP\_BS016 Revision 6  
Effective Date: 02Dec2019  
Reference: CS\_WI\_BS005

Copyright © 2009, 2010, 2012, 2016, 2018, 2019 \[REDACTED] All rights reserved. The contents of this document are confidential and proprietary to \[REDACTED] Holdings Inc. and its subsidiaries. Unauthorized use, disclosure or reproduction is strictly prohibited.

All medications will be coded using the World Health Organization (WHO) Drug Global dictionary, version B3 March 2020.

Prior and concomitant medications will be summarized by Anatomical Therapeutic Class (ATC) level 2 and preferred drug name overall and by treatment group based on the SAF analysis set. A subject having more than one medication within the same ATC Level 2 or preferred drug name will be counted only once for that ATC Level 2 or preferred drug name.

No summary will be presented for the post-study medications, but all medications (prior, concomitant, and post-study) will be listed.

## 14. EXPOSURE TO STUDY DRUG

Duration of exposure to the study drug, in days, will be summarized by treatment group based on the SAF analysis set.

### 14.1. DERIVATIONS

Duration of exposure, in days, will be calculated as follows:

- Duration of exposure (days) = (Date of last dose of study drug – Date of first dose of study drug) + 1

Interruptions to dosing will not be considered for duration of exposure.

## 15. EXPOSURE TO STUDY DRUG

Exposure to study drug, as number of doses received, total amount of drug taken (mg) and proportion of planned dose received, will be summarized by treatment group based on the SAF analysis set.

### 15.1. DERIVATIONS

Proportion of planned dose received will be calculated as follows:

- Proportion = Number of tablets taken / Number of planned tablets

Document: \[REDACTED]\net\enterprise\Apps\sasdata\SASb\SAS\Atea\_Pharmaceuticals\AT-527\SAZ\A63631\Biostatistics\Documentation\SAP\AT-03A-001\_V1.0\_COVID\_SAP\_PA7.doc  
Author: \[REDACTED]

Version Number: V1.0  
Version Date: 15Apr2021

Template No.: CS\_TP\_BS016 Revision 6

Reference: CS\_WI\_BS005

Effective Date: 02Dec2019

Copyright © 2009, 2010, 2012, 2016, 2018, 2019 \[REDACTED] All rights reserved. The contents of this document are confidential and proprietary to \[REDACTED] Holdings Inc. and its subsidiaries. Unauthorized use, disclosure or reproduction is strictly prohibited.

where:

- Number of tablets taken = (total number of tablets dispensed – total number of tablets returned)
- Number of planned tablets = 10

## 16. EFFICACY ENDPOINTS

Unless otherwise indicated, all efficacy summaries and figures will be presented by treatment group and visit, when appropriate, based on the ITT and mITT analysis set. Method to control the overall type 1 error of the study to 5% is described in [Section 7.4](#).

### 16.1. PRIMARY EFFICACY

#### 16.1.1. PRIMARY EFFICACY ENDPOINT

The primary endpoint for this study is the proportion of subjects with PRI on or before Day 14. The PRI is defined as a  $\geq$  2-tier increase from baseline in respiratory support methods required to maintain satisfactory oxygenation ( $\text{SpO}_2 \geq 93\%$ ), using the 6-tier hierarchical scale of Respiratory Support methods which have the following levels:

- LEVEL 1: Normal oxygenation on room air ( $\text{SpO}_2 \geq 93$ ), no need for supplemental  $\text{O}_2$
- LEVEL 2: Persistent hypoxemia on room air ( $\text{SpO}_2 < 93$ ) with requirement for low-level supplemental  $\text{O}_2$  by nasal cannula or mask (up to 2L/min) to maintain  $\text{SpO}_2 \geq 93$
- LEVEL 3: Requirement for higher levels of passive supplemental  $\text{O}_2$  by nasal cannula or mask ( $\geq 2\text{L/min}$ ) to maintain  $\text{SpO}_2 \geq 93$
- LEVEL 4: Requirement for oxygenation by positive-pressure devices, e.g. Continuous Positive Airway Pressure (CPAP) or Bi-level Positive Airway Pressure (BiPAP) or other non-invasive positive-pressure respiratory support methods to maintain satisfactory oxygenation and/or ventilation
- LEVEL 5: Requires invasive respiratory support (intubated mechanical ventilation or ECMO)
- LEVEL 6: Death

The assessment scores of respiratory support level are collected on the Ordinal Scale of Respiratory Support Level

Document: \[REDACTED]\net\enterprise\Apps\sasdata\SASb\SAS\Atea\_Pharmaceuticals\AT-527\ISZA63631\Biostatistics\Documentation\SAP\AT-03A-001\_V1.0\_COVID\_SAP\_PA7.doc  
Author: \[REDACTED] Version Number: V1.0  
Template No.: CS\_TP\_BS016 Revision 6 Version Date: 15Apr2021  
Effective Date: 02Dec2019 Reference: CS\_WI\_BS005

Copyright © 2009, 2010, 2012, 2016, 2018, 2019 \[REDACTED] All rights reserved. The contents of this document are confidential and proprietary to \[REDACTED] Holdings Inc. and its subsidiaries. Unauthorized use, disclosure or reproduction is strictly prohibited.

page of the eCRF (electronic Case Report Form).

### 16.1.2. MISSING DATA IMPUTATION METHOD FOR PRIMARY EFFICACY ENDPOINT

First, subjects will be declared as PRI if they have a  $\geq 2$  increase observed up to and including Day 14, even if they have some days with missing values; as long as one day has  $\geq 2$  increase they are considered PRI.

If subjects had NO recorded PRI up to Day 14 then:

- 1- If there is an observed score at Day 14 then the subject will be considered as NO PRI
- 2- If a subject discontinues without having a PRI observed prior to Day 14, they will be considered as follows:

Primary reason of early study discontinuation	PRI?
Adverse event, Death, Lack of efficacy, Lost to follow up, Non-compliance with study drug, Progressive disease, Met protocol lab criteria for discontinuation	Yes
Recovery, Pregnancy, Protocol deviation, Physician decision, Sponsor Request, Withdrawal by subject, Study terminated by sponsor	No

The assessment of the primary reason for early discontinuation will be collected on the disposition page of the eCRF

- 3- If a subject completed the study and got discharged from hospital prior to Day 14, they will be considered as NO PRI.

### 16.1.3. PRIMARY ANALYSIS OF PRIMARY EFFICACY ENDPOINT

The primary efficacy goal is to reduce the incidence of PRI by 50% for active-dosed subjects compared to placebo recipients. Number and proportion of subjects with and without PRI during the 14-day primary study period will be provided by treatment group based on the ITT analysis set. The difference between the treatment groups will be presented with corresponding 95% CI. A Cochran-Mantel-Haenszel (CMH) general association test will be used to test for differences in rates between the treatment groups controlling for geographic region (see [Section 7.6](#)).

### 16.1.4. SENSITIVITY ANALYSES FOR PRIMARY EFFICACY ENDPOINT

As sensitivity analyses to inclusion/ Exclusion criteria violation that may affect the primary analysis of the primary

Document: \\[REDACTED]\net\enterprise\Apps\sasdata\SASb\SAS\Atea\_Pharmaceuticals\AT-527\ISZA63631\Biostatistics\Documentation\SAP\AT-03A-001\_V1.0\_COVID\_SAP\_PA7.doc  
Author: [REDACTED] Version Number: V1.0  
Template No.: CS\_TP\_BS016 Revision 6 Version Date: 15Apr2021  
Effective Date: 02Dec2019 Reference: CS\_WI\_BS005

Copyright © 2009, 2010, 2012, 2016, 2018, 2019 [REDACTED] All rights reserved. The contents of this document are confidential and proprietary to [REDACTED] Holdings Inc. and its subsidiaries. Unauthorized use, disclosure or reproduction is strictly prohibited.

efficacy endpoint, the primary analysis of the primary efficacy endpoint will be repeated:

1. On mITT analysis set.
2. Excluding the subjects with symptoms for more than 5 days prior to screening.

As a third sensitivity analysis, subjects will get imputed as follows:

- 1- If  $\geq 2$  increase observed up to and including Day 14 then PRI
- 2- Else, if there is an observed score at Day 14 without PRI then NO PRI
- 3- Else, if a subject discontinues the study without having a PRI observed prior to Day 14, then PRI
- 4- Else, if subject was discharged from hospital prior to Day 14, then NO PRI

As a fourth sensitivity analysis, primary analysis of the primary efficacy endpoint will be repeated updating the imputation as follows:

If a subject discontinues without having a PRI observed prior to Day 14, they will be considered as follows:

Primary reason of early study discontinuation	PRI?
Adverse event, Death, Lack of efficacy, Lost to follow up, Non-compliance with study drug, Progressive disease, Met protocol lab criteria for Discontinuation, Protocol deviation, Physician decision, Sponsor Request, Withdrawal by subject, Study terminated by sponsor	Yes
Recovery, Pregnancy	No

The same CMH test will be performed as for the main analysis.

### 16.1.5. SUPPLEMENTARY ANALYSES FOR PRIMARY EFFICACY ENDPOINT

The following supplementary analyses will be performed for the primary efficacy endpoint:

- For each subgroup defined in [Section 7.7](#), number and proportion of subjects with and without PRI during the study of 14 days will be provided by treatment group.
- The primary analysis of the primary efficacy endpoint will be repeated to analyze the proportion of subjects

Document: \\[REDACTED]\net\enterprise\Apps\sasdata\SASb\SAS\Atea\_Pharmaceuticals\AT-527\{SZA63631\}\Biostatistics\Documentation\SAPI\AT-03A-001\_V1.0\_COVID

Author: [REDACTED] Version Number: - V1.0  
Version Date: 15Apr2021

Template No.: CS\_TP\_BS016 Revision 6

Reference: CS\_WI\_BS005

Effective Date: 02Dec2019

Copyright © 2009, 2010, 2012, 2016, 2018, 2019 [REDACTED] All rights reserved. The contents of this document are confidential and proprietary to [REDACTED] Holdings Inc. and its subsidiaries. Unauthorized use, disclosure or reproduction is strictly prohibited.

with PRI on or before Days 10, 21, 28 and 63, respectively, instead of the 14-day primary study period.

## 16.2. SECONDARY EFFICACY

### 16.2.1. KEY SECONDARY EFFICACY ENDPOINTS

#### 16.2.1.1. Change from Baseline in Quantitative SARS-CoV-2

The first key secondary endpoint is the change from baseline in amount of quantitative SARS-CoV-2 as measured by RT-PCR at the time points required in the protocol schedule of assessments (Days 2, 5, and 14). Quantitative SARS-CoV-2 will be assessed quantitatively via the TaqPath assay, and qualitatively via a separate assay, COBAS.

Analysis will be performed on the mITT analysis set only.

#### 16.2.1.2. Time to Clinical Recovery (days) by Day 14

The second key secondary endpoint is time to clinical recovery in days on or before Day 14, defined as

- Time to clinical recovery by Day 14 (days) = (Date of clinical recovery on or before Day 14 – Date of randomization) +1

Clinical recovery is defined as achieving the NIAID clinical status of level 6 or above, which include subjects who are no longer hospitalized (level 7 or 8) or hospitalized but not requiring supplemental oxygen (level 6). The clinical status and assessment date/time will be reported on the Ordinal Scale for Clinical Severity page of the eCRF.

The date of clinical recovery is based on the date the score is first  $\geq 6$ . Should there be no clinical recovery, then the time to clinical recovery is set to 15 days.

The 8 levels of NIAID are the following:

1. Death
2. Hospitalized, on invasive mechanical ventilation or ECMO
3. Hospitalized, on non-invasive ventilation or high flow oxygen devices
4. Hospitalized, requiring supplemental oxygen

Document: \\[REDACTED]\net\enterprise\Apps\sasdata\SASb\SAS\Atea\_Pharmaceuticals\AT-

527\SAZ63631\Biostatistics\Documentation\SAP\AT-03A-001\_V1.0\_COVID\_SAP\_PA7.doc

Author: [REDACTED]

Version Number: V1.0

Version Date: 15Apr2021

Template No.: CS\_TP\_BS016 Revision 6

Reference: CS\_WI\_BS005

Effective Date: 02Dec2019

Copyright © 2009, 2010, 2012, 2016, 2018, 2019 [REDACTED] All rights reserved. The contents of this document are confidential and proprietary to [REDACTED] Holdings Inc. and its subsidiaries. Unauthorized use, disclosure or reproduction is strictly prohibited.

5. Hospitalized, not requiring supplemental oxygen – requiring ongoing medical care (COVID-19 related or otherwise)
6. Hospitalized, not requiring supplemental oxygen – no longer requires close medical care for COVID-19  
(Note: Examples include recovered subjects needing inpatient quarantining/confinement or needing social services connections for outpatient living).
7. Not hospitalized, but with limitation on activities and needing close outpatient care for COVID-19 manifestations.
8. Not hospitalized, no limitations on activities, no need for continued close medical care.

#### 16.2.1.3. Proportion of Subjects with Respiratory Failure or Death (RFD) by Day 28

The third key secondary endpoint is proportion of subjects with RFD on or before Day 28, which is defined as progression to respiratory support level 5 (requiring intubated mechanical ventilation or ECMO) or 6 (death) (Section 16.1.1). The data will be reported on the Ordinal Scale of Respiratory Support Level and Death Details pages of the eCRF. Proportion of subjects with RFD on or before Days 10, 14, and 63 will also be analyzed. Missing values will be treated as follows:

- If there is no ordinal scale value because the subject discontinued prior to Day 28, then the subject will be assumed as NO RFD.
- If a subject has been discharged prior to Day 28 then they would be assumed as NO RFD.
- If a subject is still on study and in the hospital at Day 28 but with no scale score at Day 28 they will be excluded from the denominator.

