6. STUDY PROCEDURES AND GUIDELINES

Study-specific assessments and the study schedule are summarized in [Table 6-1](#). An "X" indicates when the assessments are to be performed.

Due to COVID-19 restrictions/policies/quarantines and to maintain safety of staff at individual sites and for individual subjects, it is acknowledged that strict adherence to [Table 6-1](#) for those procedures requiring direct contact with patients (such as laboratory sampling, physical examination, etc) may not be possible for every timepoint listed. The sites should try to maintain the schedule as closely and as safely as feasible, but temporal divergence for these direct contact procedures will not be considered a protocol deviation.

Hospital discharge may occur at any point. The date and time for the hospital discharge decision should be documented in the study records, as duration of hospitalization is a secondary study endpoint.

For subjects who are discharged before Day 14, assessments through Day 14 may be collected, either through at-home visits by trained medical professional(s), outpatient visits or by telephone follow-up, as feasible depending on the site and subject limitations.

If a subject is discharged before dosing is complete, the discharge plan should include completion of study drug dosing.

Protocol Number: AT-03A-001

Follow-up evaluations will occur at 7 days, 14 days and 49 days after study completion at nominal Day 14, according to the table below.

Additional logistical considerations and clarifications

- It is logistically feasible and acceptable for Screening and Day 1 to occur on the same day, as long as eligibility is confirmed before dosing is initiated. If the Screening and Day 1 visits are on the same day, duplicate assessments and laboratory samples do not need to be collected twice.
- Once subjects are confirmed eligible at Screening, randomization and dosing should be initiated within 24 hrs.

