## 7.2. MISSING DATA

Missing efficacy data will be handled as described in Sections 16.1.2, 16.2.1.2, 16.2.1.2, 16.2.1.3 and 16.2.3.6 of this analysis plan.

Missing safety data will not be imputed, except for missing AE severity and relationship data (refer to Section 17.1.1). Partial or completely missing AE and medication dates will be handled as described in APPENDIX 1.

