#### 16.2.3.3. Duration of Hospitalization for COVID-19 (days)

A secondary endpoint is the duration of hospitalization/confinement in days, defined as the time from start of treatment to either achieving Status 7 or 8 on the NIAID Clinical Status scale or hospital discharge (which ever happens first). Data from the follow-up period after Day 14 will be included. This endpoint will be calculated as follows:

- Duration of Hospitalization for COVID-19 (days) = ((Date of achieving status 7 or 8 OR hospital discharge) – Study Day 1) +1

Subjects who don't achieve status 7 or 8 nor have hospital discharge will be censored at end of study (EOS).

Subjects who die will be censored to the latest EOS date available.

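### Time to clinical recovery is dated only from ordinal-scale scores, so a subject discharged by Day 14 without a score of 6 or more is ranked as never recovered

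*SAP*

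**What the plan says.** SAP 16.2.1.2 defines clinical recovery as NIAID clinical status 6, 7 or 8, and describes 7 and 8 as subjects who are no longer hospitalized. The time is ("Date of clinical recovery on or before Day 14 – Date of randomization) +1". The source is one form: "The clinical status and assessment date/time will be reported on the Ordinal Scale for Clinical Severity page of the eCRF". The dating rule is "The date of clinical recovery is based on the date the score is first" 6 or higher, and for everyone else: "Should there be no clinical recovery, then the time to clinical recovery is set to 15 days".

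SAP 7.2 sends the reader back to the same place for missing data: "Missing efficacy data will be handled as described in Sections 16.1.2, 16.2.1.2, 16.2.1.2, 16.2.1.3 and 16.2.3.6 of this analysis plan". Section 16.2.1.2 contains no provision for discharge. The changes form of 16 March 2022 reopened this derivation to move non-recovered subjects to 15.01 days, and added none.

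The discharge information exists. Protocol section 6 states: "The date and time for the hospital discharge decision should be documented in the study records". Protocol 6.9 asks for the date and time of the discharge order in the electronic case record. SAP 16.2.3.3 uses discharge for duration of hospitalization, "defined as the time from start of treatment to either achieving Status 7 or 8 on the NIAID Clinical Status scale or hospital discharge", whichever comes first.

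**The concern.** Someone who has gone home meets the description of level 7 or 8, but the derivation sees only scores. If no score of 6 or more was entered, in hospital or afterwards, that subject gets the value also given to subjects who die or are still ill at Day 14. If the first such score comes from a later telephone call, the recovery date is the date of the call.

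Level 5 covers ongoing care for any reason, so a subject can go from 5 straight to discharge without a 6. The protocol expects some discharges during the five dosing days, and its section 6 makes assessments after discharge optional and subject to feasibility. Cases are therefore foreseeable.

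This is a key secondary endpoint, and the 2022 form keeps it in the final tables. The analysis is a rank test, so moving true recoveries to the worst rank costs power. If the two arms are affected unequally, it also biases the comparison.

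**Working it through.** **1. How discharge is treated across endpoints**

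| Endpoint | SAP section | Discharge used? |
|---|---|---|
| PRI by Day 14 | 16.1.2 | Yes: study completers discharged before Day 14 count as no PRI |
| Respiratory failure or death by Day 28 | 16.2.1.3 | Yes: counts as no event |
| Duration of hospitalization | 16.2.3.3 | Yes: discharge ends the stay |
| Time to clinical recovery | 16.2.1.2 | No |
| Kaplan-Meier sensitivity analysis of recovery | 16.2.4.2 | No: censored at the last score |

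**2. Three hypothetical subjects, each randomized on Day 1 and discharged on Day 6**
- Scored 6 on Day 6 before leaving: (6 − 1) + 1 = 6 days. Correct.
- Last in-hospital score 5, first reached by telephone on Day 10 and scored 7: (10 − 1) + 1 = 10 days. Dated four days late.
- Last in-hospital score 5, not scored again by Day 14: 15 days (15.01 under the 2022 form). Ranked with deaths.

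**3. The plan's own figures.** Inputs from SAP 7.1 and protocol Appendix 1: exponential times, medians 12 (placebo) and 7 (active) days, 91 per arm, times rounded up to whole days, anything beyond 14 set to 15, one-sided Wilcoxon test at 0.025.
- Expected placebo recoveries: 91 × (1 − 2^(−14/12)) = 91 × 0.5546 = 50.5. The SAP says about 50.
- Expected active recoveries: 91 × (1 − 2^(−14/7)) = 91 × 0.75 = 68.3. The SAP says 68.
- Simulated power, 20,000 runs: 79.8%. The SAP says 80%. All three reproduce.

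**4. Equal loss in both arms.** Let m be the share of recoveries by Day 14 that are never scored. The documents do not give m, so these values are assumptions. In the simulation a random share m of recoveries is reset to 15. At m = 10%, expected scored recoveries are 0.9 × 50.5 = 45.4 and 0.9 × 68.3 = 61.4.

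| m | Power, 91 per arm | Power, 40 per arm |
|---|---|---|
| 0% | about 80% | about 45% |
| 5% | about 76% | about 42% |
| 10% | about 71% | about 38% |
| 20% | about 61% | about 31% |

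Repeat runs differ by a point or so. Part A randomized 81 subjects, hence about 40 per arm.

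**5. Unequal loss, 91 per arm**
- Medians 12 and 7, placebo 5% / active 10%: power about 59%. At 10% / 20%: about 35%.
- No true effect (both medians 12), 10% loss in each arm: one-sided error 0.026, essentially nominal.
- No true effect, placebo 10% / active 5%: about 0.05. At 20% / 10%: about 0.10. The inflation is smaller with fewer subjects.

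**6. Medians.** The scored placebo recovery share is 0.5546 × (1 − m). It drops below one half when m exceeds 1 − 0.5/0.5546 = 9.8%. Beyond that, the expected placebo median is the assigned value.

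**The case against.** The strongest reply is that an unscored discharge departs from the schedule. Protocol 6.9 calls for daily recording of clinical status. Table 6-1 schedules the scale on every day to Day 14, and that row does not carry the footnote that waives other assessments after discharge. A score of 7 or 8 needs no physical contact, and telephone follow-up is allowed. Level 6 will also catch many recoveries before the subject leaves. All of this stands and limits the number affected. It does not remove the problem, because protocol section 6 makes post-discharge collection optional.

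A second reply is that the SAP follows protocol 8.2.2, which assigns 15 days to patients whose recovery was not observed. That is so, and the protocol wording needs attention too.

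A third is that little rests on a formal test. The hierarchy is gated on PRI, where the sponsor concedes futility; protocol 8.2.2 calls the analyses descriptive; and the 2022 form only lists Part B. This lowers the stakes but does not make the reported ranks and medians right.

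Some stronger readings are tempting but unsupported:
- *The effect is always pulled toward the null.* That assumes similar loss per recovery in both arms. More loss on placebo pushes the other way.
- *The trial loses a known amount of power, or the placebo median is no longer reached.* The shares are assumed, and 91 per arm was never enrolled in Part A. At 10% loss and 91 per arm, the placebo median is still reached by Day 14 in about half of simulated trials.
- *Leaving the study for recovery should also date a recovery.* SAP 16.1.2 does count that reason among those read as no PRI ("Recovery, Pregnancy, Protocol deviation, Physician decision, Sponsor Request, Withdrawal by subject, Study terminated by sponsor"), but the date of discontinuation is not clearly a date of recovery.

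**Conclusion.** The gap is real and lies in a stated rule: followed exactly, SAP 16.2.1.2 gives the worst rank to a subject discharged by Day 14 with no score of 6 or more, and a late date to one first scored after discharge. Subjects scored 6 or more before leaving are handled correctly, and the SAP's power figure is not itself wrong.

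The size is unknown. The power losses in the working assume that unscored recoveries are a random 5% to 20% of all recoveries, equal in both arms, under the planning medians. They show sensitivity and do not estimate what happened. The effect of late dating was not quantified. Direction is also open, since it depends on which arm has more unscored discharges.

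No safeguard remains in the final outputs. The Kaplan-Meier analysis would have censored these subjects instead of ranking them as failures, but the 2022 form drops it. The correction should be made, because it needs one derivation from data the protocol already collects.

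**What to change.** In SAP 16.2.1.2, define the recovery date as the earlier of (a) the first NIAID score of 6 or more and (b) documented hospital discharge alive, on or before Day 14. This matches the use of discharge in SAP 16.2.3.3. List the change in SAP 3.3 and align protocol 8.2.2, which now refers to recovery being observed.

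Report by arm how many subjects receive 15 (15.01) only because no score was recorded after discharge. That count shows whether the point matters in these data.

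If the change is made after unblinding, label it post hoc and show it beside the analysis as specified. Apply the same dating to the Kaplan-Meier analysis (16.2.4.2) and the Day 28 and Day 63 repeats (16.2.6) only if they are produced, since the 2022 form drops them.

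The cost is a small programming change and a protocol wording edit. The downside is that some discharges, such as transfers to another facility, may count as recoveries. The documents do not show that the eCRF records discharge destination, so the rule should not depend on it.
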